6 TREATMENT OF SUBJECTS

6.1 Study Drug(s)

6.1.1 Dosage Form and Strength

Preparation of the agents and IMP will be described in the pharmacy manual.

6.1.1.1 Agents for the Pre-randomisation Run-in Period (Part A)

The agent is a solution for subcutaneous injections (0.5 mL per injection site) of either lidocaine or placebo (saline). A dose of 2.5 mg of lidocaine will be injected per injection site.

Active doses are prepared extemporaneously at the CRU pharmacy with a marketed lidocaine hydrochloride 0.5% v/w solution for injection in 10-mL ampoules.

Placebo doses are prepared extemporaneously at the CRU pharmacy with a sterile and preservative-free sodium chloride solution 0.9% v/w solution for injection (saline) 10-mL ampoules.

The pharmacist preparing the injection syringe will be unblinded as lidocaine and placebo saline ampoules are different in appearance.

After preparation the placebo injection syringe is indistinguishable from the active lidocaine and will be appropriately labelled for immediate use.

The pharmacist will prepare 5 mL of lidocaine or placebo to inject 0.5 mL per injection site with a maximum of 10 injections in the scar pain area.

6.1.1.2 IMP for the Randomised Double-blind Period (Part B)

The IMP is a solution for single intradermal injection (0.2 mL per injection site) of either Dysport or placebo.

Active doses are prepared extemporaneously at the CRU pharmacy with marketed Dysport 500 U powder for solution for injection reconstituted and further diluted with saline to reach the targeted dose as indicated on the Dysport/placebo vial.

Placebo doses are prepared extemporaneously at the CRU pharmacy with a placebo powder for solution for injection reconstituted and further diluted with saline using the same procedure as for the corresponding Dysport dose. They are indistinguishable from the active (Dysport) formulation after reconstitution.

The pharmacist preparing the injection syringe will be blind on the treatment group and unblinded on the dose.

The pharmacist will prepare 2 mL of Dysport/placebo solution to inject 0.2 mL per injection site with a maximum of 10 injections in the scar pain area.

6.1.2 Supplies

The CRU will be provided with:

- Part A: Pre-randomisation run-in kits containing all material for injection test 1 and injection test 2 (lidocaine, lidocaine placebo (saline), injection syringes, injection syringes labels, needles).
- Part B: Randomisation kits (with the white label) and replacement kits (with the blue label) containing all material for Day 1 injection (Dysport or Dysport placebo, ampoules of saline for dilution, injection syringes, injection syringes labels, needles).

lidocaine, lidocaine placebo (saline), Dysport and Dysport placebo will be supplied with lot number, expiry date, certificate of analysis and certificate of compliance or corresponding documentation for the release of the agent and IMP.

6.1.3 Packaging and Labelling

Pre-randomisation run-in kits, randomisation and replacement kits, lidocaine, lidocaine placebo (saline), Dysport and Dysport placebo will be provided in box, vials or ampoules, labelled according to applicable regulations requirements and national laws in force.

6.1.4 Storage

The investigator, or an approved representative (e.g. pharmacist), will ensure that all agents, IMP and any other study-related materials are stored in a secured area, under recommended temperature monitored storage conditions, in accordance with applicable regulatory requirements.

Pre-randomisation run-in kits for Part A (lidocaine and lidocaine placebo (saline)) should be stored between +15°C and +25°C.

Randomisation kits for Part B (Dysport, Dysport placebo and saline used for Dysport/placebo reconstitution) should be stored between +2°C and +8°C.

6.1.5 Dispensing, Treatment and Administration Procedure

All agents and IMP provided to the CRU pharmacist will be allocated and dispensed by appropriately trained staff. Agents and IMP injections will occur under medical supervision.

[figure not shown]
Subcutaneous injections will be performed under a standard volume of 0.5 mL for lidocaine and lidocaine placebo.

Intradermal injections will be performed under a constant volume of 0.2 mL for Dysport and Dysport placebo.

A maximum of 10 sites will be injected in the scar pain area.

The scar pain area reported by the subject will be mapped and drawn on the skin with a skin marker pen. The longitudinal axis of the painful area will be measured. The boundary of the spontaneous pain felt by the subject as well as the sites for injection at 2-cm intervals and starting 1 cm from the edge of the longitudinal axis of the pain area will be marked as represented in [Figure 3](#). A photograph will be recorded with a ruler for scale and used to reproduce the administration scheme on injection test 1, injection test 2 and dosing on Day 1.

Figure 3 Administration Scheme

6.1.6 Accountability

The investigator (or designee) will ensure adequate records (allocation, disposition, shipment, dispensing and returned drugs) are maintained in an agent and IMP accountability log.

6.2 Rescue Medication

Paracetamol (acetaminophen), taken orally as required, is the rescue pain medication during the randomised double-blind period (Part B) and will be provided by the CRU to the subject. It can be taken up to four times a day and should not exceed a daily dose of 4000 mg in divided doses. A single dose of rescue medication is defined as 1000 mg (two tablets).

The single paracetamol dose may be lowered to 500 mg (one tablet) if the investigator/subject feels that the dose is higher than what may be required to provide adequate analgesic effect.

For the first week, in Part B post-dose, the investigator may substitute paracetamol with co-codamol (30 mg/500 mg, maximum 4000 mg of paracetamol per day).

If the subject takes the maximum rescue medication dose of 4000 mg paracetamol per day for three consecutive days and still reports uncontrolled scar pain, the investigator should consider discontinuing the subject from the study. If uncontrolled pain elsewhere in the body were to develop, the management of this should be handled on a case-by-case basis.

The rescue medication should be swallowed whole with water and must not be broken or crushed.

The subject will be cautioned on the use of any other medication (over-the-counter or prescription containing paracetamol e.g. Lemsip®).

Rescue medication should not be taken in conjunction with other analgesic medication unless discussed with the investigator.

If rescue medication is taken, an AE and the corresponding rescue medication should be recorded in the eCRF.

The sponsor medical monitor should be contacted if further guidance is required. For questions on concomitant medications prescribed prior to study participation, the sponsor medical monitor should be contacted before the subject is included in the study.

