3 INVESTIGATIONAL PLAN

3.1 Overall Study Design and Plan

The study will consist of two sequential parts, the first being to identify subjects who will potentially benefit from intradermal Dysport injection, 'responders', who will then progress to the second part, which is the double-blind study of the intradermal injection of Dysport or placebo:

- Part A: A double-blind, randomised, initial two-period cross-over run-in part, extended screening period of placebo or local anaesthetic (lidocaine),
- Part B: A single-dose, double-blind, randomised, parallel part with one of the three different doses of Dysport or placebo.

To ensure subjects will potentially benefit from intradermal injection of Dysport, they will be tested for responsiveness to local anaesthetic (lidocaine).

In Part A, and upon consent and successful screening of medical eligibility, subjects will be injected (injection test 1) during a pre-randomisation run-in period in a double blind fashion with either saline or local anaesthetic (lidocaine) and assessed for pain perception up to 24 hours post-injection. One week later, they will be crossed over, injected with the other agent (injection test 2) and assessed for pain perception up to 24 hours post-injection. Pain intensity will be scored using a 11-point NRS (from score 0 for "no pain" up to 10 for "worst possible pain").

If subjects are assessed as responders, they will enter in Part B, and will be trained and provided with an Actiwatch® to enable them to record twice a day their spontaneous NRS scores.

[figure not shown]
Before dosing on Day 1, the subjects will perform baseline assessments including a quantitative sensory testing (QST) assessing allodynia, hyperalgesia and conditioned pain modulation, completion of a QoL questionnaire, and safety assessments (physical examination, vital signs measurements, collection of adverse events (AEs) and recording of concomitant medication).

Subjects will be dosed if considered as consistent in pain perception from the screening visit (i.e. variability < 2 for the average spontaneous NRS score pre-injection tests in Part A, pre-QST and pre-dosing and as clinically plausible per investigator's judgement).

Subjects will then be assessed for pharmacodynamics and safety for a total of 16 weeks post-dose.

Subjects will be discharged from the study after safety assessments (physical examination, vital signs) during an end of study (EoS) visit.

The study design is presented in [Figure 2](#).

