4.4 Withdrawal of Subjects

In accordance with the declaration of Helsinki and International Council for Harmonisation (ICH) GCP, each subject is free to withdraw from the study at any time, for any reason (e.g. withdrawal of consent, AE).

The investigator can withdraw a subject from the study at any time for any reason (e.g. protocol deviation, non compliance with the protocol conditions, lack of cooperation, in the event of concurrent illness, AE, or other reasons concerning the health or well-being of the subject).

The reason for and date of withdrawal from the study must be recorded in the eCRF.

If withdrawal is based on subject's decision every attempt will be made to determine:

- The reason for withdrawal,
- Whether the subject also decides to withdraw his/her consent for the sponsor to collect and use the data collected up to the withdrawal point.

Data collected prior to subject withdrawal may be kept in study records and shared for further analyses unless the subject formally specifies his/her decision to withdraw consent for using data already collected.

Should a subject be withdrawn from the study after IMP dosing and before normal study completion, all efforts will be made to complete the EoS assessments and report the observations up to the time of withdrawal as thoroughly as possible. A complete final evaluation at the time of the subject's withdrawal should be made whenever possible.

Subjects who withdraw within the first six weeks after IMP dosing for reasons other than lack of efficacy will be replaced. Replacement subjects will receive the same schedule and treatment as the subject they have replaced.

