11.2 Sample Size Calculation

No prospective calculations of statistical power is made.

An appropriate sample size cannot be determined statistically as no previous human data from previous clinical trials are available. A sample size of six subjects per dose of Dysport has been selected. Approximately 24 subjects will be randomised in the double-blind period. Subjects who withdraw within the six first weeks from dosing will be replaced.

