		Peak-effect, i. e. maximal decrease from baseline in the spontaneous NRS score.	The mean peak in each treatment group.	
		Time to peak-effect, i.e. time to reach the peak-effect.	The mean time to reach the peak-effect in each treatment group.	
		Duration of effect, i.e. duration between time to onset and last timepoint with change from baseline in the spontaneous NRS score is ≥ 2 points.	The mean duration of effect in each treatment group (for the subjects who reach the time to onset).	

Only descriptive statistics will be provided. No statistical test will be performed.

As described in the above table, the estimand will be based on "treatment policy" strategy, which is the estimate of the treatment effect regardless of whether the subject has an intercurrent event during the study.

The following potential intercurrent events will be considered:

- The short-term use of rescue medication,
- The change in use of rescue medication.

Supplementary and sensitivity analysis will be performed to take into account these intercurrent events and to handle missing data. These analysis will be detailed in the SAP.

Analysis of the secondary endpoints

Endpoints have been defined to meet the study secondary objectives. They are presented in [Table 4](#) with their associated estimate and estimand.

Table 4 Secondary Objectives - Analysis of Secondary Endpoints

Objective	Assessments	Endpoints	Estimate of treatment effect	Estimand
To compare the efficacy of intradermal doses of Dysport to placebo.	Spontaneous pain as assessed by the spontaneous NRS score.	Change from baseline in the spontaneous NRS score to each scheduled timepoint.	Difference between each Dysport doses and the placebo group, in the mean change from baseline in the spontaneous NRS score to each scheduled timepoint.	For each estimate, the associated estimand will be based on "treatment policy" strategy (i.e. regardless of the intake of rescue medication).
	Stimulus-evoked pain as assessed by the NRS score during QST.	Change from baseline in the stimulus-evoked NRS score to each scheduled timepoint.	Difference between each Dysport doses and the placebo group, in the mean change from baseline in the stimulus-evoked NRS score to each scheduled timepoint.	For each estimate, the associated estimand will be based on "treatment policy" strategy (i.e. regardless of the intake of rescue medication).
To assess the safety and tolerability of a range of intradermal doses of Dysport	Refer to Section 11.3.1 .			

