Duration of effect (in days) i.e. duration between time to onset and last timepoint with decrease from baseline in the spontaneous NRS score is \geq two points Derivation: Duration is calculated as: last timepoints for which change from baseline ≤ -2 – time to onset (in days)	The mean duration of effect in each treatment group (for the subjects who reach the time to onset)

Each endpoint will be evaluated using the worst pain within the last 12 hours and using the averaged pain within the last 12 hours.

5.7.3.2 *Primary Analysis*

For each estimate, analysis will be based on the treatment policy estimand: No adjustment will be made in case of intake of rescue medication. No handling of missing data will be performed in the primary analysis.

Listings will be provided including all subjects with missing values for the 4 primary endpoints based on the NRS score. For subjects with missing values, the listings will provide all observed data related to the primary endpoints i.e. all measurements recorded prior to the missing value, any measurements recorded after the missing value, important baseline characteristics, the reason for study discontinuation and the timing of study discontinuation.

Summary table for time to onset, peak-effect, time to peak effect and duration of effect will be computed for each assessment, by treatment group and Placebo versus all Dysport groups.

The number and percentage of subjects who reach the time to onset will be presented for each assessment, by treatment group.

For each assessment, scatter plots and box whisker plots will be generated for the comparison of the peak effects between the treatment groups and all Dysport groups.

5.7.3.3 *Sensitivity Analysis*

The same analyses as described in section 5.7.3.2 will be performed on the PP population using the uncorrected parameters if important differences, i.e. at least 2 patients in the same treatment group, between the randomised population and the PP population are observed: the need for this analysis will be discussed during the blind data review meeting.

5.7.3.4 *Supplementary Analysis*

Not applicable.

5.7.3.5 *Subgroup Analysis*

No subgroup analyses will be performed.

5.7.4 *Randomised double-blind period: Analysis of Key Secondary Efficacy Endpoints*

5.7.4.1 *Endpoint, Treatment Effect and Estimand Definition*

To assess the secondary objectives, the treatment policy estimand is defined by the following key attributes:

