5.7.5.2 Analysis

Quality of Life

A listing of individual responses to the SF-36 questionnaire will be prepared.

For each question of the SF-36 questionnaire, a summary table presenting the raw scores and change from baseline will be generated by dimension, treatment group and measurement time.

Arithmetic means of the global scores will be presented on a histogram by treatment group, with all visits and dimensions on the same graph. Arithmetic means of the

global scores will also be presented on a histogram by dimension, with all visits and treatment group on the same graph.

Individual histograms presenting mean scores by dimension and visit will be produced, with all dimensions on the same graph.

Rescue Medications

A listing of rescue medications will be provided, including the total amount of rescue medication and the time from D1 to first intake of rescue medication.

Summary of count and percentages of subjects having at least one rescue medication will be provided by ATC class and preferred Name, by treatment group.

Summaries of the total amount of rescue medication by preferred Name and the time to first intake (in days) will be provided by treatment group and Placebo group versus all Dysport groups. The number of subjects using a rescue medication and the number of rescue medication taken will also be described by treatment group.

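### Discontinuation for uncontrolled pain on maximum rescue ends data collection in a single-dose study, although the estimand is treatment policy regardless of rescue; the replacement rule for such exits is also inconsistent

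*Protocol*

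**What the plan says.** Protocol 3.1 describes Part B as "A single-dose, double-blind, randomised, parallel part with one of the three different doses of Dysport or placebo", with 16 weeks of follow-up. Under Protocol 6.2, rescue paracetamol "should not exceed a daily dose of 4000 mg in divided doses". If a subject is at that maximum on three consecutive days and "still reports uncontrolled scar pain, the investigator should consider discontinuing the subject from the study". The action named is leaving the study, not stopping a treatment.

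Protocol 11.3.3.2 bases the estimands in Tables 3, 4 and 5 on treatment policy, "which is the estimate of the treatment effect regardless of whether the subject has an intercurrent event during the study". It lists two intercurrent events, short-term rescue use and a change in rescue use. It promises supplementary and sensitivity analyses for these events and for missing data.

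SAP 5.7.3.2 states: "No handling of missing data will be performed in the primary analysis". SAP 2.6 withdraws the promised sensitivity analyses, citing little rescue use and difficulty linking scores to rescue, subject to confirmation at the blind data review. SAP 5.7.4.3 plans none for the secondary endpoints.

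For the rescue endpoint, SAP 5.7.5.2 plans "Summaries of the total amount of rescue medication by preferred Name".

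On replacement, Protocol 4.4 says: "Subjects who withdraw within the first six weeks after IMP dosing for reasons other than lack of efficacy will be replaced". Protocol 11.2 says: "Subjects who withdraw within the six first weeks from dosing will be replaced".

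**The concern.** A treatment-policy estimand needs the scores recorded after the event it disregards. Section 6.2 offers a route by which heavy rescue use with uncontrolled pain leads to no further scores. No study treatment remains to be stopped after Day 1, so what ends is observation.

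The primary objective is to describe a time course, and a shortened record cannot show a later onset or peak. With six subjects per arm and no tests, the descriptive means are the result, so one or two informative exits can matter. The rescue total is cut short in the same subjects. The replacement conflict leaves open whether such a subject is followed by a new one on the same treatment.

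**Working it through.** **1. Arm size.** Randomisation is 3:1:3:1:3:1 in blocks of 12 (Protocol 3.4.1.2). Two blocks give 2 × 3 = 6 subjects per Dysport dose and 2 × (1 + 1 + 1) = 6 on pooled placebo, so 24 in all. This reproduces the planned number. One subject is 1/6 = 16.7% of an arm.

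**2. What stops at exit.**
- Protocol 4.4 asks for the EoS assessments and observations up to withdrawal.
- Protocol 5.2.4 brings the EoS visit forward.
- Protocol 9.1.3 runs Actiwatch collection only to EoS.
- The schedule in Protocol 18.1 has no QST or SF-36 in the W16 EoS/ED column, so any remaining Week 6 and Week 12 values are lost.
- No collection after discontinuation is described.

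**3. Effect on the primary endpoints (definitions in SAP 5.7.3.1).** For one subject, compare the shortened record with the full one:
- Peak effect is the minimum change over the timepoints. A minimum over fewer points cannot be lower, so the observed peak effect is unchanged or smaller.
- Time to peak is unchanged or earlier.
- Onset is unchanged if it came before exit. Otherwise it is never seen, and the proportion reaching onset is unchanged or lower.
- Duration is unchanged or shorter if onset was seen. If it was not, the subject drops out of the mean duration.

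**4. Effect on by-timepoint means (SAP 5.7.4.2).** If k of 6 subjects leave and their change would have been g NRS points worse than that of the others, the observed-case mean looks better by (k/6) × g. The documents give no SD or exit rate, so k and g are assumptions.

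| k | g = 1 | g = 2 | g = 3 |
|---|---|---|---|
| 1 | 0.17 | 0.33 | 0.50 |
| 2 | 0.33 | 0.67 | 1.00 |

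**5. Direction.** Suppose exits are commoner on placebo. By step 4, later placebo means look better and the Dysport difference shrinks. By step 3, the mean observed placebo peak effect stays the same or falls, so the Dysport difference in peak stays the same or widens. If exits fall mainly on a Dysport arm, both directions reverse.

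**6. Rescue total = daily amount × days observed.**
- Exit after 3 days at the maximum: 3 × 4 g = 12 g. The same rate over 16 × 7 = 112 days would be 448 g, so 12/448 = 2.7% is recorded.
- Completer taking 1 g every second day: 56 × 1 g = 56 g, or 0.5 g/day.
- The first subject uses 4/0.5 = 8 times as much per day but has the lower total.
- At 4 g/day, 56 g is reached after 56/4 = 14 days. Exit at Week 6 would record 42 × 4 = 168 g. The reversal against this comparator is therefore confined to exits before two weeks.

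**7. Replacement wording, place by place.**
- Lack-of-efficacy withdrawals excepted: synopsis row on statistical methodology; Protocol 4.4.
- No exception: synopsis row on planned number of subjects; Protocol 11.2; SAP 2.3. The examples in Protocol 3.4.1.2 and SAP 2.4.2 are also unqualified.

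**The case against.** **Section 6.2 is not rescue censoring.** A reader might infer that it contradicts the estimand outright. It does not. A subject who takes rescue and stays keeps every score. Leaving creates missing data, which the listed intercurrent events do not cover. The rule is also discretionary and needs both maximum use and uncontrolled scar pain, so it does not reach every heavy user. This stands, and it makes the point a gap in data collection and not a flat contradiction.

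**The size is unknown.** A reader might infer a large and one-sided loss. For example, assumed placebo changes of 0, 0, -1, -1.5, -1.5 and -2 average -1.0, but -1.5 if the two non-improvers leave. Against an assumed Dysport mean of -2.5, the difference falls from -1.5 to -1.0. Nothing in the documents supports two such exits in six, SAP 2.6 points to little rescue use, and the direction is different for peak effect.

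**Dropout will be visible.** SAP 5.7.3.2 lists subjects with missing primary endpoints, with the reason for and timing of discontinuation. SAP 5.7.4.2 shows group sizes over time and individual profiles, and flags scores on rescue days. Pre-exit data are kept, and SAP 6.2 assigns the withdrawal visit to the next empty visit. This helps interpretation but does not recover the lost scores.

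**The rescue endpoint is exploratory.** Time to first intake and number of users are also reported, and a per-day figure could be derived from the exposure duration in SAP 5.8.2. It is not planned, however.

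**Scores after a change in analgesia are harder to attribute to Dysport.** This is true, and it is a cost of the treatment-policy strategy that the protocol chose.

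**Conclusion.** The point holds as a gap between Protocol 6.2 and the data that Tables 3 to 5 require. The SAP leaves the gap open by not handling missing data and by dropping the sensitivity analyses.

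Each exit affects 16.7% of an arm. On the assumption that those who leave are 1 to 3 NRS points worse than those who stay, later arm means shift by 0.17 to 0.50 for one loss and 0.33 to 1.00 for two. How many exits occur is unknown and may be few. The documents do not support a claim of bias in a single direction, nor a claim that rescue totals are generally reversed; that reversal needs a very early exit. The replacement conflict is plain on the wording and separate from the bias question; it bears only on exits in the first six weeks.

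**What to change.** - Reconcile Protocol 6.2 with Tables 3 to 5 on data collection only, leaving the clinical decision and the prohibited-medication rules in 5.3.4 as they are. State that a subject to whom the 6.2 rule is applied will be asked, with consent, to continue Actiwatch scoring and the scheduled W6, W12 and W16 assessments, with later analgesics recorded.
- State in the SAP that these scores stay in the treatment-policy analysis and are flagged in the listings.
- Report rescue amount per day of observation beside the planned total.
- State one replacement rule in both synopsis rows, Protocol 3.4.1.2, 4.4 and 11.2, and SAP 2.3 and 2.4.2.

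The cost is protocol and consent wording, a few SAP lines, and visits that are already scheduled. Some subjects will decline, and scores after a change in analgesia say less about Dysport's own effect.
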